Later, to evaluate if there were differences between the groups of treatment after the intervention on the variables of interest, deltas were generated from the Kujala test, EVA, number of squats, Q angle, balance, physical activity and core strength. with iron and trunk extension, evaluating normality by means of graphic and numerical methods. For the analysis of the differences of medians between the groups, taking into account that the outcomes did not present a normal distribution, and assuming the assumption of independence of the variables, we proceeded to use the non-parametric Mann-Whitney U test. Finally, through the Wilcoxon test, intragroup differences were evaluated for strength, pain and physical activity components.

The hypothesis tests were presented in two tails with an alpha of 0.05 and all the analyzes were executed with the statistical program STATA version 14.0.

BASELINE:

Study population

Therapeutic Effect of Two Muscle Strengthening Programs in Patients with Patellofemoral Pain Syndrome

Table 5 describes the general characteristics of the study population at baseline. There were no significant differences between the two intervention groups (A and B), which means that the randomization was adequate; however, in the total score of the Kujala test there was a difference of 12.5 points between the groups, with a lower score for group B (53.0), which indicates better core strength for these patients. Finally, the sex variable was defined as categorical and the rest of the variables as continuous, for which the medians and their respective interquartile range (IR) are reported, taking into account that the variables did not have a normal distribution.

Table 5: Baseline variables of the study population

Variables	Treatment A (n 20) Medium (RI)	Treatment B (n 20) Medium (RI)	Value p ^a
Sex * (Male, Ref)			
Female	90 (65.7-97.6) *	90.0 (65.7-97.6) *	1,000 ^b
Age	32.5 (25.5-38.0)	29.0 (25.0-36.5)	0,569
Initial weight (Kg)	64.6 (55.3-72.4)	62.7 (52.9-68.5)	0.379
Size (cm)	160 (156.5-167.0)	159.5 (154.0-163.0)	0.423
IMC	25.4 (21.5-27.9)	23.8 (22.3-25.2)	0.456
% of fat	35.4 (28.9-40.4)	35.4 (24.5-38.7)	0,714
% muscle	26.9 (24.5-28.9)	26.2 (24.6-29.0)	0.849
Visceral fat	6 (3.5-7.09)	5 (4.0-6.0)	0.433
IPAQ (minutes)	3003 (1116-4638)	1617 (944-6138)	0,588
Pain	7.5 (5.5-9.0)	7.0 (5.5-8.5)	0.764
Kujala total score	65.5 (42.5-72.5)	53.0 (44.5-71.5)	0,892
Q angle			
Straight	19.0 (15.0-20.0)	18.0 (15.0-20.0)	0,557

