To evaluate the effect of muscle strength on the alignment of the knees and analyze the effect of muscle strength on the unipodal balance, **Table 8** shows the deltas of the medians (changes or differences observed after the intervention) for each of the treatment groups and for each of the variables measured at the beginning and end of the intervention.

In this way, when they include or add exercises for the strengthening of the core, to the traditional treatment of SPF or anterior knee pain, the quality of life measured with the Kujala test in these patients increases, especially by the significant reduction of pain, highlighting for example, that for the total score of the Kujala test, there was a statistically significant difference ($p = 0.025$), with an increase of 5 points for group A (group A = 23.0, group B = 17.0), which indicates that the population of the study group improved their quality of life more after the intervention compared with the people of group B. A similar effect is observed in the increase of the strength of the core musculature for group A, especially in the oblique force evaluated with the side plate, with a difference of 30 seconds for group A, and only five seconds for group B on the left lateral plate, with a statistically significant p value (<0.001).

Therapeutic Effect of Two Muscle Strengthening Programs in Patients with Patellofemoral Pain Syndrome
On the other hand, the differences for the total pain evaluated with EVA were -6 and -4 for group B, with an interquartile range (-10; -4) and (-7; -3) respectively. Although p was not statistically significant, these differences were clinically relevant. For the hip and knee muscle strength, measured with the squat test, there was no statistically significant difference in the median of the deltas between the treatment groups, but there was one in each group, which means that all of them increased strength muscle in hips and knees, as a result of strengthening for these muscle groups.

Table 8: Effect of muscle strengthening on pain, knee alignment, core, hip and knee strength and balance by treatment groups.

Variable	Treatment A			Treatment B			Value p *
	Initial Medium (RI)	Final Medium (RI)	Delta Medium (RI)	Initial Medium (RI)	Final Medium (RI)	Delta Medium (RI)	
Pain (EVA)	7.5 (5.5-9.0)	2 (0-2)	-6 (-10; -4)	7.0 (5.5-8.5)	2.0 (0-4)	-4 (-7; -3)	0.058

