In **Table 9**, differences in medians and interquartile ranges their entire study population at the beginning and end of treatment for muscle strength, pain and level of physical activity is. It can be seen that the gluteal and quadriceps muscle strength measured with the squat test at the end of the treatment was the same in both groups, with a statistically significant p value (<0.001), which means that the whole population increased strength in a significant way.

In the same way, a similar effect was observed in the median pain measured with the VAS at the end of the treatment, because they all reported a decrease in pain, this difference being statistically significant, with a p-value less than 0.001. However, in the measurement of physical activity level with the long IPAQ at the end of the treatment, it was observed that the study population in group B spent less time practicing physical activity at the beginning of treatment, but both groups increased in time similar this practice at the end of the treatment; however, this difference was not statistically significant.

Table 9: Difference of intragroup medians for muscle strength, pain and physical activity level.

Variable	Treatment A			Treatment B		
	Initial Medium (RI)	Final Medium (RI)	Value p *	Initial Medium (RI)	Final Medium (RI)	Value p *
Squats	10.0 (8.0-18.5)	35.0 (30.0-38.0)	<0.001	12.5 (8.5-20.0)	35.0 (29.0-38.0)	<0.001
IPAQ (minutes)	3003 (1116-4638)	4275 (2587-6522)	0.029	1617 (944-6138)	4598 (2888-7344)	0.012
Pain (EVA)	7.5 (5.5-9.0)	2.0 (0.0-2.0)	<0.001	7.0 (5.5-8.5)	2.0 (0-4)	<0.001

* Wilcoxon nonparametric test

Muscular Strength and Static Balance

In **Table 10**, the correlation between the muscle and gluteus muscle strength differences measured with the squat and unipodal balance test evaluated with the One Leg Stance test with open and closed eyes by treatment groups is shown, with which it is emphasized that, for both treatment groups, the unipodal balance improved clinically significant. However, for the study group (A), this correlation was greater (strong), especially in the variable with open eyes for both lower limbs, indicating that by increasing muscle strength (glutes and quadriceps in this case) it is improved the unipodal balance. Although there is an increase in the balance for both treatment groups, there is a stronger correlation when core exercises are included, which is what happens in group A.

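### Table 10 does not support crediting core exercises with a stronger strength–balance correlation: the difference between arms was not tested, and core-strength change is not in the table

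*SAP*

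**What the plan says.** Under Bivariate Analysis, the SAP states that "deltas were generated from the Kujala test, EVA, number of squats, Q angle, balance, physical activity and core strength", to be compared between arms by the Mann-Whitney U test. Spearman correlation is planned for pairs of continuous variables, overall and within each arm, with Q angle and knee pain as the example. The squat–balance correlation is not named there, and no method is given for comparing a coefficient between arms. For tests in general, "The hypothesis tests were presented in two tails with an alpha of 0.05".

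Table 8 is titled "Effect of muscle strengthening on pain, knee alignment, core, hip and knee strength and balance by treatment groups". It reports the squat count, three plank measures, trunk extension and four one-leg balance measures.

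Table 10, under Muscular Strength and Static Balance, is introduced as the correlation between "muscle and gluteus muscle strength differences measured with the squat and unipodal balance test"; it correlates change in squats with change in balance, separately by arm. The text calls the arm A correlation strong, especially with eyes open, and ends with "there is a stronger correlation when core exercises are included, which is what happens in group A".

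**The concern.** The closing sentence moves from two separate within-arm coefficients to a statement about what core exercises do. It needs evidence that the coefficients differ between arms by more than chance, and none is given. A coefficient near 0.55 in one arm and near 0.1 in the other looks like a clear contrast, but with about 20 patients each coefficient is very imprecise.

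The sentence also names core work, while the strength variable is the squat count. The strength measures that did respond differently by arm, the planks and trunk extension, do not appear in Table 10.

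At stake is a secondary conclusion: a reader would take away that adding core work links strength gains more closely to balance gains.

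**Working it through.** **Inputs**
- Table 10 coefficients, as printed. They need patient-level data, so they cannot be reproduced here; nor can the Mann-Whitney p-values in Table 8.
- Patients per arm: 20 at baseline (Table 5). The number at follow-up is not printed, so 20 is an assumption; 16 to 20 is shown.
- Two-sided alpha of 0.05, from the SAP.

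**Step 1. Test of the A–B difference in correlation**

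Transform each coefficient: f(r) = ½ ln[(1 + r)/(1 − r)].

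Test statistic: z = [f(r_A) − f(r_B)] / √(v_A + v_B), with v = 1.06/(n − 3), a usual variance for Spearman's coefficient.

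At n = 20 per arm the standard error is √(2 × 1.06/17) = 0.353.

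| Balance measure | r, arm A | r, arm B | f(A) − f(B) | z | p |
|---|---|---|---|---|---|
| Right, eyes open | 0.558 | 0.121 | 0.630 − 0.122 = 0.508 | 1.44 | 0.15 |
| Left, eyes open | 0.554 | 0.110 | 0.624 − 0.110 = 0.514 | 1.45 | 0.15 |
| Right, eyes closed | 0.390 | 0.009 | 0.412 − 0.009 = 0.403 | 1.14 | 0.25 |
| Left, eyes closed | 0.008 | −0.244 | 0.008 + 0.249 = 0.257 | 0.73 | 0.47 |

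- *Other variance formulas* at n = 20, 1/(n − 3) and (1 + r²/2)/(n − 3), give p of 0.14–0.15, 0.13–0.15, 0.24–0.25 and 0.45–0.46. Nothing changes.
- *Fewer patients* (1.06 variance): at 18 per arm p = 0.18, 0.17, 0.28 and 0.49; at 16 per arm p = 0.21, 0.20, 0.32 and 0.52.

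**Step 2. Precision**

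For right eyes open, the 95% limits come from f(r) ± 1.960 × √(1.06/17) = f(r) ± 0.489, transformed back. Arm A: 0.14 to 0.81. Arm B: −0.35 to 0.54. Arm A's interval excludes zero and arm B's does not, but that is not a test of whether the two differ.

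Power to separate 0.558 from 0.121 at 20 per arm is Φ(1.44 − 1.96) ≈ 0.30. For 80% power, n = 2 × 1.06 × [(1.960 + 0.842)/0.508]² + 3, about 68 per arm.

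**Step 3. The direct comparison in Table 8**

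| Balance change | Median, A | Median, B | p |
|---|---|---|---|
| Right, eyes open | 11.5 | 7.5 | 0.916 |
| Left, eyes open | 9.5 | 20.0 | 0.282 |
| Right, eyes closed | 20.0 | 19.0 | 0.671 |
| Left, eyes closed | 24.5 | 20.0 | 0.349 |

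No difference is detected, and the left eyes-open medians point towards arm B.

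**Step 4. Eyes-open balance**

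Final eyes-open balance is 45.0 (45.0-45.0) on both sides in both arms. The printed quartiles put at least half of each arm at 45.0 (the middle of the distribution, from lower to upper quartile), and the repeated value suggests a cap. For a patient who ends at 45, change equals 45 minus baseline. The two largest coefficients in Table 10 may therefore largely reflect baseline balance.

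**Step 5. Core strength**

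Median changes, A v B, in Table 8: prone plank 37 v 10, right side plank 30 v 6, left side plank 30 v 5, trunk extension 49 v 15 seconds, with p <0.001, <0.001, <0.001 and 0.001. None of these is correlated with balance in the documents.

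**The case against.** Table 10 is open about its scope. Its column is headed as squats, the text says glutes and quadriceps, and the paragraph before Intragroup differences ties that part of the analysis to hip and knee strengthening common to both arms. The sentence can be read as pure description: the arm that did core work has the larger coefficients, which is true for all four measures. With about 30% power, a non-significant test does not show that the correlations are equal. All of this stands, but none of it supports crediting core exercises.

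A reader might also infer more than the documents allow:

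- *That the plan defined muscle strength as core plus hip and knee and later narrowed it.* The list of deltas names squats and core strength separately, and no composite is defined. The planned Wilcoxon step, in which "intragroup differences were evaluated for strength, pain and physical activity components", does not say which strength measures it covers. This is loose labelling.
- *That squat change cannot show an effect of core work because its median change is 20.0 in both arms (p = 0.670).* A within-arm correlation does not depend on the arm's median, so two arms with the same squat change can have different squat–balance correlations. Nor does p = 0.670 prove equal change.
- *That the core–balance analysis was never run, or that arm B's core gains were hidden.* The documents show only that the correlation is not reported. Table 8 prints arm B's initial, final and change values for all four core measures.

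**Conclusion.** The sentence crediting core exercises with a stronger correlation is unsupported. On the printed coefficients none of the four A–B differences is near significance (p about 0.15, 0.15, 0.25 and 0.47), the balance changes themselves show no detected difference between arms, and the two largest coefficients come from a measure that looks capped. The evidence is inconclusive; it does not show that the correlations are the same.

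This rests on 20 analysed patients per arm and on a normal approximation for Spearman's coefficient, which is rough where many values tie at 45. Fewer patients would raise the p-values.

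The consequence is limited to this secondary conclusion. The between-arm comparisons of pain and Kujala score do not depend on Table 10.

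**What to change.** 1. For each Table 10 correlation, print the number analysed, a 95% confidence interval for each arm, and an interval and test for the A–B difference. Because of the ties at 45, a bootstrap that resamples patients within arm is safer than the normal approximation. Label the table exploratory.
2. Replace the sentence on core exercises with that result, followed by the Table 8 finding of no detected difference between arms in balance change. State that eyes-open balance appears to be at a ceiling.
3. If a statement about core strength and balance is wanted, add the correlations of the four core changes with the four balance changes as exploratory. That is 4 × 4 = 16 coefficients, so multiplicity and the ceiling should be noted. These answer a different question from item 1 and do not replace it.
4. Label the strength rows of Tables 9 and 10 as squat count. Adding core rows to Table 9 is optional.

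The cost is a short analysis of data already held and some rewording. The price is that the core-and-balance statement is withdrawn unless the new results support it.

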## INTERVENTION PROTOCOL

From the following scheme (Scheme 3), each training session of the muscle strengthening program was structured for each of the intervention groups, which was based on the principles of training and the Earl and Hoch protocol described in the theoretical framework.

*Scheme 3: A y B Strengthening Program*

After the adjustments described in the pilot test, the strengthening program was applied to the forty patients who were previously randomized to the intervention protocols for groups A and B.

Each of the exercise sessions lasted approximately 45 to 60 minutes, of which, the first 8 to 10 minutes were dedicated to the initial warm-up exercises, the same for program A and B, which gave way to the phase central to the session, that is to say the strengthening exercises: group B took about five minutes less to complete it, because they performed an exercise less than group A in each of the three phases set out in the program; This phase of strengthening lasted approximately 20 to 30 minutes of the total session.

Each session was divided into four parts, of which the second part (central strengthening phase) included between 24 and 28 exercises in total, group A and B respectively. In addition to this, the anatomical conditioning phase was carried out in two weeks, in which 5 to 6 strengthening exercises were prescribed depending on the treatment group, but for both groups the volume was two sets of 10 repetitions, with approximately 30 seconds rest between sets and between exercises, with an execution speed of 1/1 (concentric / eccentric contraction ratio) that allowed patients to adapt to adequate movement control and therefore, joint protection.

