[name]

NCT04011436

Therapeutic Effect of Two Muscle Strengthening Programs in Patients with Patellofemoral Pain Syndrome

**Therapeutic Effect of Two Muscle Strengthening
Programs in Patients with Patellofemoral Pain
Syndrome from Bogota, Colombia.
Experimental Study, Clinical Controlled Trial.**

NCT: 04011436

Date of creation: July 1, 2018.

PROCESSING AND DATA ANALYSIS.

For the classification and verification of the information, the database was refined by recoding and labeling the variables necessary for the analysis, in addition, the variables that required it were converted to alphanumeric format and the review of extreme non-plausible data was performed. For the continuous variables in which two attempts were made as balance and plate a new variable was generated with the average of the measurements and in this way obtain the final result for the analyzes.

Univariate Analysis

The report of absolute and relative frequencies was made; the qualitative variables were presented in proportions and 95% confidence intervals. The normality of the continuous variables was evaluated by scatter plots (histograms, Kernel density and Q-Norm) and the numerical test of Shapiro-Wilk, and according to their distribution they were reported as means and standard deviations, when they had a distribution normal, or on the contrary, as medians and interquartile ranges.

Bivariate Analysis

In the bivariate analysis, a comparison of each of the Kujala test domains was initially performed to assess pain in the baseline, assessing the differences between the intervention groups using the chi-square or Fisher's exact tests. Additionally, the Spearman correlation coefficient was used to evaluate the relationship between two continuous variables, such as the Q angle and the anterior knee pain, evaluating the correlation in a marginal and conditioned way to each of the treatment groups.

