Table 10: Correlation between differences in muscle strength and balance by treatment groups

Therapeutic Effect of Two Muscle Strengthening Programs in Patients with Patellofemoral Pain Syndrome

Variable	Squats	
Balance	Treatment A *	Treatment B *
Right with open eyes	0,558	0.121
Left with open eyes	0,554	0.110
Right with closed eyes	0.390	0.009
Left with closed eyes	0.008	-0.244

* Spearman correlation coefficient.

With the previously stated results, the alternative hypothesis of this study is rejected, which means that adding core exercises to traditional hip and knee muscle strengthening for the treatment of anterior knee pain in patients diagnosed with SPF is more effective in reducing pain and improving the quality of life of these people, they do only hip and knee strengthening exercises.

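### The strength-and-balance conclusions drawn from Table 10 go beyond eight within-arm correlations: none of the four A-versus-B contrasts reaches p < 0.05, and the causal reading is unsupported

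*SAP*

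**What the plan says.** Table 10 of the SAP ("Correlation between differences in muscle strength and balance by treatment groups") gives Spearman coefficients between the change in squats and the change in one-leg stance time: four balance measures in each of two arms. Its only footnote names the coefficient.

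The text introducing the table, under Muscular Strength and Static Balance, says that "for the study group (A), this correlation was greater (strong), especially in the variable with open eyes", takes this as "indicating that by increasing muscle strength (glutes and quadriceps in this case) it is improved the unipodal balance", and ends with "there is a stronger correlation when core exercises are included, which is what happens in group A".

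The methods under Bivariate Analysis plan Spearman coefficients overall and by arm, "evaluating the correlation in a marginal and conditioned way to each of the treatment groups". The between-arm test there ("we proceeded to use the non-parametric Mann-Whitney U test") applies to the change scores, not to the correlations. The stated error level is explicit: "The hypothesis tests were presented in two tails with an alpha of 0.05".

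**The concern.** Two inferences are drawn that the table cannot carry.

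- **Arm contrast.** A difference in correlation between arms is linked to the core exercises. That is a comparison of arms, but no such comparison was planned or reported, and no measure of precision is given. With at most 20 patients per arm, a gap between two correlations can be large and still be compatible with chance.
- **Cause.** A correlation of two change scores within an arm is read as strength gain improving balance. Randomisation does not protect this relation: it assigned programmes, not amounts of strength gain. Common drivers such as adherence or baseline level are not examined.

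A reader would take away a mechanism (strength drives balance) and an added effect of core exercises on it. Neither was tested.

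**Working it through.** **Inputs.** Coefficients from Table 10. Two-sided alpha 0.05 from Bivariate Analysis. n = 20 per arm is an assumption for Table 10: it is the baseline n in Table 5 and the maximum available, since "the strengthening program was applied to the forty patients who were previously randomized to the intervention protocols for groups A and B". The SAP states no test result for these correlations, so there is no figure of its own to reproduce.

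**Contrast between arms.** z = (atanh rA - atanh rB) / sqrt(vA + vB), with three choices of variance v: 1/(n - 3) (Fisher), 1.06/(n - 3) (adjusted for Spearman) and (1 + r²/2)/(n - 3) (Bonett-Wright).

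Example, right leg, eyes open, Fisher variance: atanh 0.558 = 0.630 and atanh 0.121 = 0.122, a difference of 0.508. The standard error is sqrt(2/17) = 0.343, so z = 0.508/0.343 = 1.48 and p = 0.138.

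The CIs below use 1.06/(n - 3). The CI of the difference combines the limits of the two single CIs. The p range covers the three variances.

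| Balance measure | A (95% CI) | B (95% CI) | A - B (95% CI) | p |
|---|---|---|---|---|
| Right, open | 0.558 (0.14 to 0.81) | 0.121 (-0.35 to 0.54) | 0.44 (-0.16 to 0.97) | 0.138-0.154 |
| Left, open | 0.554 (0.13 to 0.81) | 0.110 (-0.36 to 0.54) | 0.44 (-0.16 to 0.98) | 0.134-0.150 |
| Right, closed | 0.390 (-0.08 to 0.72) | 0.009 (-0.45 to 0.46) | 0.38 (-0.27 to 0.94) | 0.240-0.254 |
| Left, closed | 0.008 (-0.45 to 0.46) | -0.244 (-0.63 to 0.24) | 0.25 (-0.41 to 0.85) | 0.454-0.467 |

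**Sensitivity to n.** A smaller n only raises p: the smallest of the four is 0.174 at n = 17 per arm and 0.208 at n = 15. With the printed coefficients, p < 0.05 would need 33-36 per arm (right, open), 33-35 (left, open), 51-54 (right, closed) or 120-127 (left, closed). All exceed 20.

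**Single coefficients.** t = r × sqrt((n - 2)/(1 - r²)) on 18 df. In A: p = 0.011, 0.011, 0.089 and 0.973, in table order. In B: 0.611, 0.644, 0.970 and 0.300. So only A's two eyes-open coefficients differ nominally from zero, with no allowance for eight coefficients.

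**The causal reading against the trial's other figures.**

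- The protocol gave both arms the same one-foot balance work, 8 exercises of 30 to 45 seconds, so balance was also practised directly.
- In Table 8 the median squat gain is 20.0 in both arms. In B, balance rose by medians of 7.5 to 20.0 s while its correlations with squat gain run from -0.244 to 0.121.
- The largest median balance gain in Table 8 (A, left, eyes closed, 24.5 s) goes with a correlation of 0.008.
- Final eyes-open time is 45.0 (45.0-45.0) on both legs in both arms. Both quartiles equal the median, which suggests a ceiling. For every patient who finished at 45.0, the change is simply 45.0 minus baseline, so the two coefficients that the text stresses may largely reflect baseline balance.

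**The case against.** The strongest reply is that the text never claims a significant difference between the correlations. It says the correlation was greater in A, all four rows show that, and reporting coefficients by arm is what the methods planned. As a description of the sample this is true. But the closing sentence ties the difference to the inclusion of core exercises, and that is an inference about the programmes.

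The causal wording could be loose translation, since the SAP describes its Q-angle correlations in similar terms. Even so, the natural reading is causal.

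Two of the supporting arguments have limits. Balance training prescribed identically to everyone cannot by itself create a within-arm correlation; only variation in adherence or response could, and the documents give no data on either. A large median gain beside a correlation near zero does not refute an effect of strength either, because a median gain and a rank correlation measure different things. These points show that the stated pattern is not general; they do not show that strength has no effect.

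The four contrasts all point the same way, and separate tests ignore that. The rows come from the same patients, so they cannot be combined as if independent.

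The ceiling deserves weight, because it touches the only two nominally non-zero coefficients. The labels also clash: the SAP calls -0.545 and -0.548 moderate in its Q-angle section, yet calls 0.558 and 0.554 strong here.

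**Conclusion.** The concern holds. Table 10 supports an exploratory association in arm A between squat gain and eyes-open balance gain (r about 0.55, unadjusted p about 0.011 on each leg). It does not support a stronger link with core exercises: no contrast falls below p = 0.13. It does not support the statement that strength gain improves balance.

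The contrast result assumes n = 20 per arm and standard approximations for Spearman coefficients; it is the same under all three variances and at every smaller n tried. It is not evidence of equal correlations. Power at the observed eyes-open gap is only about 30%, and the CIs reach almost 1.

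The reach is limited. The between-arm comparisons of balance change in Table 8 (p = 0.282 to 0.916) answer a different question and can stand. The closing conclusion on pain and quality of life does not rest on Table 10.

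**What to change.** 1. In Table 10, add the n per arm, a 95% CI for each coefficient, and for each row the A-minus-B difference with its CI and p value.
2. Delete the two statements or reword them as exploratory. For example: in arm A, larger squat gains went with larger eyes-open balance gains; the difference from arm B was not statistically significant; both arms trained one-leg balance.
3. Add a caution that final eyes-open time was 45.0 (45.0-45.0) in both arms, which suggests a ceiling and may tie the change to baseline.
4. Use one label for correlations of about 0.55 throughout.
5. Keep the Mann-Whitney comparisons of balance change in Table 8 as the between-arm balance result.

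The cost is a short calculation on existing data and a secondary conclusion weakened or lost. The added contrast is unplanned and has low power, so it must be shown with its CI and not offered as proof of no difference.

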Kujala total test score	65.5 (42.5-72.5)	88.0 (81.0-95.0)	23.0 (16.0-37.0)	53.0 (44.5-71.5)	78.0 (64.0-88.0)	17.0 (8.0-24.0)	0.025
Squats	10.0 (8.0-18.5)	35.0 (30.0-38.0)	20.0 (18.0-25.0)	12.5 (8.5-20.0)	35.0 (29.0-38.0)	20.0 (15.0-24.0)	0.670
IPAQ (minutes)	3003 (1116-4638)	4275 (2587-6522)	1539 (807-2457)	1617 (944-6138)	4598 (2888-7344)	1977 (1191-2815)	0,492
Q angle							
Straight	19.0 (15.0-20.0)	18.0 (15.0-20.0)	0 (-2; 2)	18.0 (15.0-20.0)	18.0 (15.0-20.0)	0 (-2; 2)	0.819
Left	18.0 (15.0-20.0)	18.0 (16.0-20.0)	0 (-2; 2)	18.0 (15.0-20.0)	18.0 (15.0-20.0)	0 (-2; 2)	0.672

Balance with open eyes							
Straight	30.0 818.25- 45.0)	45.0 (45.0- 45.0)	11.5 (0- 25.5)	40.0 (18.25- 45.0)	45.0 (45.0- 45.0)	7.5 (0- 30.0)	0.916
Left	29.5 (15.75- 44.0)	45.0 (45.0- 45.0)	9.5 (0- 21.5)	25.75 (14.5- 45.0)	45.0 (45.0- 45.0)	20.0 (0- 30.0)	0.282
Balance with closed eyes							
Straight	4.5 (3.0- 9.259)	28.5 (21.0- 35.0)	20.0 (14.0- 27.5)	5.25 (3.0- 7.25)	23.5 (16.5- 31.5)	19.0 (9.5- 24.0)	0.671
Left	5.0 (3.0- 8.7)	30.0 (23.5- 38.0)	24.5 (13.0- 30.5)	4.25 (3.5- 7.259)	27.5 (14.0- 34.5)	20.0 (10.5- 30.5)	0.349
Griddle	20.5 (12.0- 32.0)	60.0 (45.0- 70.0)	37.0 (24.0- 48.0)	30.0 (13.5- 33.5)	35.0 (20.0- 60.0)	10.0 (2.0- 15.0)	<0.001
The t. Right	15.0 (10.0- 21.0)	45.0 (38.0- 51.0)	30.0 (19.0- 36.0)	15.0 (9.5- 20.0)	22.0 (16.0- 38.0)	6.0 (2.0- 12.0)	<0.001
The t. Left	12.5 (10.5- 19.0)	45.0 (36.0- 56.0)	30.0 (17.0- 40.0)	18.0 (11.0- 23.0)	21.0 (15.0- 34.0)	5.0 (-2 - 10.0)	<0.001
Trunk extension	13.5 (6.0- 26.5)	61.0 (50.0- 75.0)	49.0 (30.0- 55.0)	13.5 (2.5- 20.0)	30.0 (15.0- 60.0)	15.0 (7.0- 34.0)	0.001

* U of Mann-Whitney for the delta of the measurements between the groups.

He was also interested in this research, to observe the intra-group differences of including hip and knee muscle strengthening exercises (conventional physiotherapeutic treatment) performed in the same way for both intervention groups, as mentioned in the description of the strengthening protocol.

Intragroup differences

Therapeutic Effect of Two Muscle Strengthening Programs in Patients with Patellofemoral Pain Syndrome

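### Table 8 shows no between-arm difference in one-leg balance, the text never says so, and the core-exercise benefit implied from the Table 10 correlations is unsupported

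*SAP*

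**What the plan says.** The SAP's Bivariate Analysis section makes balance one of the outcomes compared between arms: "deltas were generated from the Kujala test, EVA, number of squats, Q angle, balance, physical activity and core strength". For that comparison, "we proceeded to use the non-parametric Mann-Whitney U test", and "The hypothesis tests were presented in two tails with an alpha of 0.05". The Protocol (Intervention Protocol) refers to "forty patients who were previously randomized to the intervention protocols for groups A and B", so this is the randomised comparison.

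Post-Intervention Results introduces Table 8 partly to "analyze the effect of muscle strength on the unipodal balance". The table footnote defines its p-values: "U of Mann-Whitney for the delta of the measurements between the groups". The table has four balance rows: right and left leg, eyes open and eyes closed.

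The text on Table 8 discusses Kujala, side plank, pain and squats. It says openly that pain and squats did not differ significantly between arms. It gives no between-arm result for balance.

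Balance returns under Muscular Strength and Static Balance, which introduces Table 10 (Spearman correlations of squat change with balance change, by arm). That text says balance improved in both groups, calls the group A correlation strong, and ends: "Although there is an increase in the balance for both treatment groups, there is a stronger correlation when core exercises are included".

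**The concern.** Whether adding core exercises changes balance is answered by comparing balance change between the randomised arms. That test was planned, run and tabulated, and it shows no difference in any row. The narrative passes over it and links balance to core work through a different statistic.

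A within-arm correlation shows whether patients who gained more squats also gained more balance. It does not show whether one arm gained more balance than the other. A reader who relies on the text could conclude that core exercises helped balance, on the strength of a statistic that cannot show it.

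**Working it through.** **1. The stated results.** All figures are from SAP Table 8 and Table 10; gains are median deltas in Table 8's units, read here as seconds.

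| Row | Gain A | Gain B | A minus B | Table 8 p | r in A | r in B |
|---|---|---|---|---|---|---|
| Right, eyes open | 11.5 | 7.5 | +4.0 | 0.916 | 0.558 | 0.121 |
| Left, eyes open | 9.5 | 20.0 | -10.5 | 0.282 | 0.554 | 0.110 |
| Right, eyes closed | 20.0 | 19.0 | +1.0 | 0.671 | 0.390 | 0.009 |
| Left, eyes closed | 24.5 | 20.0 | +4.5 | 0.349 | 0.008 | -0.244 |

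None of the four p-values is below 0.05; the smallest is 0.282.

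**2. Rough check of Table 8.** The Mann-Whitney p-values cannot be reproduced without patient data. As an approximation, take mean = (Q1 + median + Q3)/3, SD = IQR/1.349 and SE = √[(SD_A² + SD_B²)/20]. The 20 per arm is an assumption, because the post-intervention number is not stated.

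Example, right leg, eyes closed:
- Mean A = (14.0 + 20.0 + 27.5)/3 = 20.5; mean B = (9.5 + 19.0 + 24.0)/3 = 17.5; difference 3.0.
- SDs 13.5/1.349 = 10.0 and 14.5/1.349 = 10.7; SE = 3.3.
- 95% interval 3.0 ± 1.96 × 3.3, that is -3.4 to 9.4 (unrounded SE).

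| Row | Approx. difference in means (95% interval), s | Approx. p |
|---|---|---|
| Right, eyes open | -0.2 (-13.0 to 12.6) | 0.98 |
| Left, eyes open | -6.3 (-18.3 to 5.7) | 0.30 |
| Right, eyes closed | 3.0 (-3.4 to 9.4) | 0.36 |
| Left, eyes closed | 2.3 (-6.3 to 11.0) | 0.60 |

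The approximate p-values do not match the printed ones closely with eyes closed, but all four agree in being well above 0.05. The intervals are wide. The normal approximation is weakest with eyes open, where the distribution is bounded.

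**3. Possible ceiling with eyes open.** Both arms finish both eyes-open rows at 45.0 (45.0-45.0). If 45 s is the test maximum (an inference), the gain is bounded by the starting value. Room to 45 from the baseline medians:
- Right: A 45 - 30.0 = 15.0; B 45 - 40.0 = 5.0.
- Left: A 45 - 29.5 = 15.5; B 45 - 25.75 = 19.25.

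In each row the arm with more room has the larger median gain. These two rows therefore say little about core exercises in either direction.

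**4. What Table 10 can show.**
- Its strength variable is squat change, which the SAP describes as gluteal and quadriceps strength. No core measure enters. Squat gain did not differ between arms (median 20.0 in both, p = 0.670).
- A higher correlation does not imply a larger gain. On the left leg with eyes open, A has the higher correlation and the smaller median gain.
- The Protocol states that the neuromuscular (static balance) component was the same in both arms, so improvement in both does not credit core work.

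**5. Do the correlations differ between arms?** The SAP reports no such test, and Table 10 has no intervals. Fisher z: z = [atanh(r_A) - atanh(r_B)]/√[2/(n - 3)], with n = 20 assumed, so the denominator is √(2/17) = 0.343.
- Right, eyes open: (0.630 - 0.122)/0.343 = 1.48, p = 0.138.
- Left, eyes open: (0.624 - 0.110)/0.343 = 1.50, p = 0.134.
- Right, eyes closed: (0.412 - 0.009)/0.343 = 1.17, p = 0.240.
- Left, eyes closed: (0.008 + 0.249)/0.343 = 0.75, p = 0.454.

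With n from 17 to 20 per arm and two variance corrections for Spearman coefficients, p runs from 0.13 to 0.51. No row shows a difference at two-sided 0.05.

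**The case against.** The SAP text is more guarded than a quick reading suggests. A reader might infer that it states a wrong result for balance. It does not: it never says group A gained more, and it attributes better balance to glute and quadriceps strength. The closing conclusion names only pain and quality of life.

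A reader might also infer selective reporting. All four rows are printed in full, with p-values and a footnote naming the test. The narrative gap is not peculiar to balance, since the Q-angle comparison is not described in the Table 8 text either.

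The correlations also have a legitimate place. The SAP plans Spearman correlations overall and by arm, with Q angle and pain as its example, and the aim stated for Table 8 concerns the effect of muscle strength on balance.

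All of this stands and limits the point to the narrative. It does not rescue the clause on core exercises, which goes beyond a strength-balance relation and draws a contrast between arms that was never tested. Nor does it explain why pain and squats are reported as non-significant and balance is not.

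**Conclusion.** The planned between-arm test showed no difference in balance change in any of four rows (p = 0.916, 0.282, 0.671, 0.349), and the text does not report it. The benefit implied for core exercises is unsupported: the correlations contain no core measure, do not compare gains, and do not differ detectably between arms (approximate p = 0.134 to 0.454).

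Two further readings should be avoided. The result does not show that core exercises have no effect on balance, because the approximate intervals span several seconds each way and the eyes-open rows may be at a ceiling. Nor does the larger left eyes-open gain in B favour B: it is not significant (p = 0.282), and B started lower.

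The printed p-values rest on no assumption of this review. The intervals and Fisher z tests assume 20 patients per arm after treatment and approximate normality. This is a correction worth making to the text on a listed outcome; it does not touch the trial's stated conclusion.

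**What to change.** - In the text on Table 8, state that no between-arm difference in one-leg balance was shown. Give the four p-values, each with an effect estimate and 95% confidence interval from the patient data (a Hodges-Lehmann shift would match the Mann-Whitney test), and the number analysed per arm.
- Note there that both arms finish eyes open at 45.0 (45.0-45.0), so those rows may be limited by a ceiling. Do not present the larger left eyes-open gain in B as a finding.
- Under Muscular Strength and Static Balance, delete the clause that ties the stronger correlation to core exercises, and label Table 10 exploratory.
- Leave the closing conclusion unchanged on this account.

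The cost is a few sentences and one short run on existing data. The downside for the sponsor is that the text becomes slightly less favourable to program A.
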